- (c) Control of tissue regeneration: swelling, wound closure, colour of the implantation site
- (d) Membrane performance: barrier effect, membrane exposition

* X-Ray performed at pre-inclusion or inclusion visit (before the surgery)

IV.4. INFORMATION TO PARTICIPANTS

During pre-inclusion visit, the Investigator (a qualified individual) will ask the participant and/or the legal guardians/legal representative to participate in the research project and provide him/her/them with information regarding:

- The objective, the description of the surgery and,
- The automatic processing of participant-related data that will be collected during the research project, and shall also specify the participant's right to access, object to, or rectify the data.

The Investigator will also ensure that the eligibility criteria are met. If a person agrees to participate, he or she will sign the consent form included at the end of the patient information sheet. His or her non-opposition to data use will be recorded and stored in his or her medical file. The participant may, at any moment, oppose the use of his or her data as part of the research.

IV.5. FOLLOW-UP VISITS

- V -1, pre-inclusion visit (-1 month to Day 0):
 - Signature of the written consent
 - Inclusion / Exclusion criteria
 - Demographic data
 - Life habits: smoker
 - Relevant medical and surgical histories
 - X-Ray

- Periodontal clinical examination
- V 0, inclusion visit:
 - X-Ray (Pre-surgery, if not performed at pre-inclusion visit)
 - Periodontal surgery, tooth extraction, alveolar filling
 - Evaluation of product stability and usability
 - Safety evaluation by the record of any adverse event
- V 1 and V 2 at 1, 2 weeks post-surgery (\pm 2 days):
 - Control of soft tissue regeneration
 - Membrane performance
 - Safety evaluation by the record of any adverse event

IV.6. END OF RESEARCH PROJECT VISIT

- V 3 at 12 weeks (± 1 week):
 - Control of soft tissue regeneration
 - Membrane performance
 - X-Ray
 - Safety evaluation by the record of any adverse event

V. STUDY POPULATION

V.1. INCLUSION CRITERIA

- Male or female aged 18 to 70
- Periodontal defects (e.g. cyst, bone tumour, crest augmentation...)
- Alveolar bone defect after tooth (teeth) extraction
- Non Opposition form (consent of the patient)
- Patients affiliated to the French social security
- Patients not under guardianship or judicial protection

V.2. EXCLUSION CRITERIA

- Pregnancy or breastfeeding women

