- Requires hospitalization or prolongation of existing hospitalizations: AE requires at least an overnight admission or prolongs a hospitalization beyond the expected length of stay. Hospital admissions for surgery planned before study entry, for social reasons, for any elective surgery (i.e. plastic surgery) or for normal disease management (including treatment adjustment) are NOT to be considered as SAE according to this criterion;
- A persistent or significant disability/incapacity or substantial disruption of the ability to conduct normal life functions;

- A congenital anomaly/birth defect;
- An important medical event: AE that may not result in death, be life-threatening, or require hospitalization may be considered an SAE when, based upon appropriate medical judgment, they may jeopardize the patient and may require medical or surgical intervention to prevent one of the outcomes listed above.

The Investigator must continue to follow the patient until the SAE has subsided or until the condition becomes chronic in nature, stabilizes (in the case of persistent impairment), or the patient dies.

VII.3.3. CLASSIFICATION OF AN ADVERSE EVENT

VII.3.3.1. SEVERITY OF EVENT

The severity of AEs must be assessed by the Investigator according to the following definitions. The term "severity" is used to describe the intensity of a specific event. This has to be distinguished from the term "serious".

- Mild: Events require minimal or no treatment and do not interfere with the participant's daily activities.
- Moderate: Events result in a low level of inconvenience or concern with the therapeutic measures. Moderate events may cause some interference with functioning.
- Severe: Events interrupt a participant's usual daily activity and may require systemic drug therapy or other treatment. Severe events are usually potentially life-threatening or incapacitating. Of note, the term "severe" does not necessarily equate to "serious".

VII.3.3.2. Relationship to study product

The clinician must always determine the relationship between all adverse events and the investigated medical device by examinating and evaluating the participant on the basis of temporal relationship between the AE and application of the device and his/her clinical judgment. In a clinical trial, the investigated medical device must always be suspected. The degree of certainty about causality will be graded using the categories below:

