• Definitely Related: There is clear evidence to suggest a causal relationship, and other possible contributing factors can be ruled out. The clinical event, including an abnormal laboratory test result, occurs in a plausible time relationship to study intervention administration and cannot be explained by concurrent disease or other drugs or chemicals. The response to withdrawal of the study intervention (dechallenge) should be clinically plausible. The event must be pharmacologically or phenomenologically definitive, with use of a satisfactory rechallenge procedure if necessary.

- Probably Related: There is evidence to suggest a causal relationship, and the influence of other factors is unlikely. The clinical event, including an abnormal laboratory test result, occurs within a reasonable time after administration of the study intervention, is unlikely to be attributed to concurrent disease or other drugs or chemicals, and follows a clinically reasonable response on withdrawal (dechallenge). Rechallenge information is not required to fulfill this definition.
- Potentially Related: There is some evidence to suggest a causal relationship (e.g., the event occurred within a reasonable time after administration of the trial medication). However, other factors may have contributed to the event (e.g., the participant's clinical condition, other concomitant events). Although an AE may rate only as "possibly related" soon after discovery, it can be flagged as requiring more information and later be upgraded to "probably related" or "definitely related", as appropriate.
- Unlikely to be related: A clinical event, including an abnormal laboratory test result, whose temporal relationship to study intervention administration makes a causal relationship improbable (e.g., the event did not occur within a reasonable time after administration of the study intervention) and in which other drugs or chemicals or underlying disease provides plausible explanations (e.g., the participant's clinical condition, other concomitant treatments).
- Not Related: The AE is completely independent of study intervention administration, and/or evidence exists that the event is definitely related to another etiology. There must be an alternative, definitive etiology documented by the clinician

VII.3.3.3. EXPECTED ADVERSE EVENTS

The most frequent adverse events expected from RCM observed in patients are:

- Post-operative infection
- Discomfort
- Irritation
- Fever
- Inflammatory reaction

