- Allergy

Some side effects may be treated with medication or require reoperation.

VII.3.4. ADVERSE EVENTS REPORTING

Complete and accurate data on all AEs experienced for the duration of the reporting period, will be reported in the eCRF.

It is important that each AE report includes a description of the event, whether it is considered serious, its duration (onset and resolution dates), its severity, its relationship to the investigational product, any other potential causality factors, any treatment given or other action taken and its outcome.

As defined in Article R5212-17 of the French Public Health Code, all incident or risk of incident resulting from the use of a medical device brought to the investigator's attention will be the subject of a spontaneous report from the investigator to the local vigilance correspondent on whom he depends or, failing that, to the French National Agency for the Safety of Health Products (Agence Nationale de Sécurité et du Médicament = ANSM) in accordance with the usual procedures in force.

These declarations should be addressed at :

Direction de la surveillance – Plateforme de réception et d'orientation des signalements E-mail: [contact] [contact]

All AEs occurring from the time of informed consent until end of study participation must also be reported to the Sponsor.

All AEs that the Investigator considers related to the medical device occurring after the end of study participation must be reported to the Sponsor.

To report the AE, the AE form can be filled. When the form is completed, signed and dated, it must be sent to the Sponsor, specifically to the vigilance contact:

Vigilance contact :

[name] Quality Assurance Manager E-mail: [contact] [contact]

Immediately after receiving the follow-up information, the Investigator must update the AE form and submit any supporting documentation (e.g., patient discharge summary or autopsy reports) to the Sponsor.

For any research involving the human, where an unexpected serious adverse reaction or a new fact relevant to the research or product under investigation is likely to prejudice to the safety of the appropriate persons, the proponent and the Investigator shall take appropriate urgent safety measures.

VII.3.5. NEW FACTS REPORTING

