AE reporting will focus on TEAEs. TEAE will be summarised and detailed using descriptive statistics by:

- seriousness,
- intensity,
- action taken with investigational product,
- other action taken,
- relationship to study treatment,
- severity according to the relationship with patient identifications

The number/frequency of patients with each TEAE will be displayed by System Ogan Class and Preferred Term according to Medical Dictionary for Regulatory Activities (MedDRA) classification.

All SAEs will be listed separately with the same information that the TEAE.

VIII.4.4. RADIOGRAPHIC ANALYSIS

The radiographic analysis of periodontal tissues will be reviewed and analysis by the clinical expert and the coordinating investigator.

The radiographic data will be recorded in the eCRF. The description of the radiographic analyses and the presentation of these results will be in a separate document from the statistical report produced by the CRO.

VIII.4.5. BASELINE DESCRIPTIVE STATISTICS

Descriptive statistics of demographics and other baseline characteristics will be presented on the FAS population.

VIII.4.6. RELEVANT MEDICAL AND SURGICAL HISTORIES

Relevant medical and surgical histories will be determined by the Investigator and will be describe on the FAS population.

Relevant medical and surgical histories will be coded using MedDRA dictionary (latest version available) and will be describe using descriptive statistics by:

- Number (percentages) of subjects with relevant medical histories
- Number (percentages) of relevant medical histories by subject
- Number (percentages) of relevant medical histories and number (percentages) of subjects with relevant medical histories by SOC
- Number (percentages) of relevant medical histories and number (percentages) of subjects with relevant medical histories by SOC and by PT

VIII.4.7. EXPLORATORY ANALYSES

For exploratory purposes, factors associated with improved performance such as age, relevant medical and surgical histories and life habits will be investigated using logistic regression.

VIII.5. PLANNED INTERIM ANALYSES

One interim analysis is planned in this study protocol in order to obtain the first results for December 2019. This study is descriptive, no randomized, open-label and single arm, so no alpha inflation or adjusted p-value are to be considered.

VIII.6. SUB-GROUP ANALYSES

No sub-group analysis is planned

IX. DATA ACCESS RIGHTS AND SOURCE DOCUMENTS

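### Causality is graded against the membrane only, on a scale that steers early procedure-caused events to at least Potentially Related, so the related-TEAE summary cannot separate membrane from surgery and may overstate the membrane's share

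*Combined protocol and SAP*

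**What the plan says.** Section VII.3.3.2 sets a single causality question: "The clinician must always determine the relationship between all adverse events and the investigated medical device". The judgement is made "on the basis of temporal relationship between the AE and application of the device and his/her clinical judgment". The reminder to suspect the device comes next, "In a clinical trial, the investigated medical device must always be suspected", and then five grades:

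- *Definitely Related*: other contributors are ruled out, and the event is one that "cannot be explained by concurrent disease or other drugs or chemicals".
- *Probably Related*: an influence of other factors is unlikely.
- *Potentially Related*: there is some evidence of a link, with reasonable timing given as the example; other contributing factors are allowed.
- *Unlikely*: the timing makes a causal link improbable, and drugs, chemicals or underlying disease offer a plausible explanation.
- *Not Related*: the event is independent of the intervention or clearly due to something else, and a definitive alternative cause must be documented.

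There is no matching scale for the surgery, the extraction or a bone filler. Yet IV.5 lists for the inclusion visit "Periodontal surgery, tooth extraction, alveolar filling", and the synopsis has the membrane covering the defect with or without prior filling.

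VII.3.4 asks that each report give "its relationship to the investigational product, any other potential causality factors". VIII.4.3 summarises TEAEs on the Safety Set by "relationship to study treatment" and sets severity against relationship. It plans nothing by relationship to the procedure. IV.1 describes the study as single-arm and non-comparative.

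**The concern.** The first secondary objective (III.2) is the safety of the membrane. VII.3.3.3 lists the events expected from it: infection after the operation, discomfort, irritation, fever, inflammation and allergy. Most of these could also follow the surgery with no membrane in place. The documents do not say so, but it is a reasonable inference.

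With no comparator there is no background rate to subtract. The investigator's attribution at the time of reporting is then the only information that could distinguish membrane from procedure, and the scale asks about one of the two only. At stake is the reading of one safety table: a count of related TEAEs could be taken as the membrane's contribution when much of it belongs to the operation. A genuine membrane signal could also be hidden among procedure events carrying the same grade.

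**Working it through.** **1. Following the scale for one event.** Take local inflammation a few days after surgery that the procedure in fact caused.

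- *Not Related* needs a documented definitive alternative cause. Ordinary inflammation around a fresh membrane will seldom supply one.
- *Unlikely* joins two conditions. The timing condition fails by construction, because the membrane went in during the operation and anything early after surgery is equally early after the device. The explanation condition names drugs, chemicals and disease; its bracketed examples mention concomitant treatments, which might be stretched to cover surgery, but the timing condition would still fail.
- *Potentially Related* is met: the timing is reasonable and other factors may have contributed.
- *Probably* and *Definitely Related* should not be used if the investigator recognises the surgery as a likely contributor.

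Read literally, the event lands at *Potentially Related*. This is a consequence of the wording, not of careless grading.

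**2. The plan's own figures.** The documents state no adverse-event or relatedness rate, so nothing specific to this point can be reproduced. The recruitment figure, used below, does reproduce: 1.96 × √(0.9 × 0.1 / 50) = 8.32% (stated 8.3%), and 50 / 0.9 = 55.6, so 56 patients (stated 56).

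**3. Illustration of scale (all rates are assumptions).** Let d be the true proportion of patients with a membrane-caused event, b the proportion with a similar procedure-caused event, and m the share of the latter graded *Potentially Related* or higher. Then

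apparent related rate = d + (1 − d) × b × m.

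With d = 2% and all 56 patients receiving the membrane:

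| b | m | Calculation | Rate | Patients of 56 | Exact 95% CI |
|---|---|---|---|---|---|
| any | 0 | 0.02 | 2.0% | 1 | 0.0–9.6% |
| 10% | 0.5 | 0.02 + 0.98 × 0.05 | 6.9% | 4 | 2.0–17.3% |
| 10% | 1 | 0.02 + 0.98 × 0.10 | 11.8% | 7 | 5.2–24.1% |
| 20% | 0.5 | 0.02 + 0.98 × 0.10 | 11.8% | 7 | 5.2–24.1% |
| 20% | 1 | 0.02 + 0.98 × 0.20 | 21.6% | 12 | 11.6–34.4% |
| 30% | 0.5 | 0.02 + 0.98 × 0.15 | 16.7% | 9 | 7.6–28.3% |
| 30% | 1 | 0.02 + 0.98 × 0.30 | 31.4% | 18 | 20.3–46.0% |

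With m = 0 there is no inflation. In five of the six rows with m above zero, the apparent rate exceeds 9.6%, the upper limit around one patient in 56. Under these assumptions the grading rule can matter more than sampling error. The table shows sensitivity; it does not estimate what the study will find.

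**The case against.** The strongest reply is that the instruction to suspect the device is not a grade. It tells the investigator to consider the membrane; the degree of certainty is then graded on five levels, two of them negative, and the upper two exclude events with other likely contributors. This stands. A reader might infer that every post-operative sign will be counted as device-related; the text does not require that.

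Second, the safety endpoints in VIII.4.3 are AEs and SAEs. Relationship is one of several descriptive breakdowns, and no device-related event rate is named as an endpoint. Summaries by System Organ Class, Preferred Term, seriousness and intensity do not depend on attribution. This also stands.

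Third, other causal factors are recorded (VII.3.4), and VIII.4.1 promises a description of all variables and individual listings, with a separate SAP still to come. This stands in part. The item would at least be listed, and the documents do not show whether it is coded or free text. But it has no grading scale and no planned cross-tabulation, so no device/procedure split follows from it.

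Fourth, over-attribution makes the membrane look worse, not better, and a second judgement by the same investigator cannot fully separate things done in one session. Both are fair, and they lower the urgency. Section II.2 itself accepts, for the cited studies, that results belong to the whole procedure.

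**Conclusion.** The concern holds in a limited form. The scale is one-sided for early events, so the summary by relationship cannot separate membrane from procedure and may overstate membrane-related TEAEs. This rests on the wording of the grades, on the shared timing of membrane and surgery, and on the inference that the expected events can follow surgery alone.

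The size is unknown, because the documents give no rate. It depends on the share of procedure events graded related, and is nil if investigators set the literal wording aside and grade them all *Unlikely* or *Not Related*. It also depends on which grades are read as related, which VIII.4.3 does not define; the illustration counts *Potentially Related* and above.

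A reader might go further and call the safety result of this single-arm study uninterpretable. The documents do not support that: all-cause TEAEs and SAEs remain a valid description of the whole procedure with the membrane. Nor do they support any particular count of falsely attributed patients. The change is worth making, but the study does not stand or fall on it.

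**What to change.** - **AE form and VII.3.3.2:** add a second graded item for relationship to the surgical procedure, covering extraction and any bone filler, beside the existing item for the device.
- **VII.3.3.2:** name the procedure as an admissible alternative explanation in *Unlikely* and *Not Related*, so that plausible timing alone does not rule these grades out.
- **VIII.4.3 and the SAP:** on the Safety Set, tabulate patients with TEAEs related to device only, procedure only, both or neither. State which grades count as related, and present all-cause TEAEs as the main safety result.

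The cost is one eCRF field, a few words in the scale and one table; the sample size is unchanged. The downside is one more unblinded judgement per event. Many early events may fall under both, so the split is descriptive and does not replace a control arm. Because VII.3.4 makes reporting after the end of participation depend on device-relatedness, the revision should state how that duty applies under the reworded grades.

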- Occurrence of any medical condition or circumstance that exposes the patient to substantial risk and/or does not allow the patient to adhere to the requirements of the protocol;
- Any SAE, clinically significant adverse event, which indicates to the Investigator that continued participation is not in the best interest of the patient;
- Pregnancy;
- Patient failure to comply with protocol requirements or study-related procedures; or
- Termination of the study by the Sponsor or the regulatory authority.

In the case of patients lost to follow-up, attempts to contact the patient must be made and documented in the patient's medical records.

Withdrawn patients will not be replaced.

VI. STUDY INTERVENTION

VI.1. **DEVICE DESCRIPTION**

This medical device is a Resorbable Collagen Membrane intended for use in Guided Tissue Regeneration or Guided Bone Regeneration procedures.

The Resorbable Collagen Membrane is crosslinked according to a controlled manufacturing process in accordance with current standards. Type I and III collagen fibres are extracted from the porcine epidermis and purified.

The Resorbable Collagen Membrane is hydrophilic and provides a barrier function for 12 weeks to prevent colonization of the surgical site by cells of connective and epithelial tissues.

The Resorbable Collagen Membrane allows the diffusion of biological fluids for a total resorption in 24 weeks.

The Resorbable Collagen membrane is easy to handle. Flexible, it adapts perfectly to all bone geometries.

The Resorbable Collagen Membrane is available in several dimensions: 15x25mm, 20x30mm and 30x40mm.

VI.2. INTENDED USE

The Resorbable Collagen Membrane is intended for use in Guided Tissue Regeneration or Guided Bone Regeneration procedures.

The claimed performance of the Resorbable Collagen Membrane is as follows: a barrier function that prevents the colonization of bone defect by connective and epithelial tissues.

VI.3. SURGICAL INTERVENTION

The Resorbable Collagen Membrane is indicated for the treatment of oral and maxillofacial bone defects and in periodontal diseases. This membrane is exclusively reserved for adults. It has not been tested on pregnant or breastfeeding women.

During this study, the investigators' practices will not be modified. For each type of surgery, the surgeon will perform all his acts in accordance with his current practice, without adding any additional procedure.

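### The top two causality grades rest on a response to withdrawal, which a membrane placed once and left in place cannot routinely show

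*Combined protocol and SAP*

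**What the plan says.** Section VII.3.3.2 (Relationship to study product) defines five grades. Three matter here.

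- *Definitely Related*: clear evidence, other causes ruled out, plausible timing, and then "The response to withdrawal of the study intervention (dechallenge) should be clinically plausible". The event must also be definitive on pharmacological or phenomenological grounds, with rechallenge if necessary.
- *Probably Related*: other causes unlikely, reasonable timing, "and follows a clinically reasonable response on withdrawal (dechallenge". The definition then adds "Rechallenge information is not required to fulfill this definition", so rechallenge is waived and dechallenge is not.
- *Potentially Related*: some evidence of a causal link, with no dechallenge element, but with the rider "However, other factors may have contributed to the event".

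The lead-in to the scale asks the clinician to judge on timing relative to application of the device and on clinical judgment, and to suspect the device always.

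On the device, section VI.1 says: "The Resorbable Collagen Membrane allows the diffusion of biological fluids for a total resorption in 24 weeks". The background in section II.2 counts the absence of a second operation for removal as an advantage of resorbable membranes. Section VII.2 has adverse events recorded from screening to the 12-week visit (± 1 week). Section VIII.4.3 summarises treatment-emergent events by, among other attributes, "relationship to study treatment".

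**The concern.** Safety is a secondary objective, and section II.5 expects the study to confirm an acceptable balance of benefit and risk. The breakdown by relationship is the part of the safety output that speaks to the device itself rather than to the whole operation. If the two strongest grades depend on an observation that this device seldom allows, the breakdown partly reflects the scale.

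The wording shows where the scale came from: it speaks of trial medication, of other drugs or chemicals, and of events being pharmacologically definitive. For a drug, stopping treatment and watching the event resolve is an ordinary observation. For a membrane under the mucosa it is not. What is at stake is whether a reader can take the split between grades at face value.

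**Working it through.** The plan gives no figure to reproduce on this point. The check is a reading of the definitions plus one subtraction.

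**1. Can resorption act as the withdrawal within follow-up?** Total resorption is at 24 weeks (VI.1). The final visit is at 12 ± 1 weeks (VII.2), so between week 11 and week 13.

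- Latest final visit: 24 − 13 = 11 weeks before total resorption.
- Earliest final visit: 24 − 11 = 13 weeks before total resorption.

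Complete resorption therefore falls outside the recording period for every patient. Section VII.3.2 extends follow-up for serious events until they subside or stabilise, which could run longer, but this applies to serious events only.

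**2. Is there another route to a dechallenge?** No removal is planned. Section VII.3.3.3 foresees that some side effects may require reoperation, but does not mention taking the membrane out. A dechallenge is thus possible in exceptional cases and absent as a routine.

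**3. Apply the definitions to a test case.** Take an inflammatory reaction at the implantation site, with plausible timing, other causes excluded, and the membrane still in place.

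| Grade | Evidence and timing | Other causes | Response to withdrawal | Result read literally |
|---|---|---|---|---|
| Definitely | met | ruled out, as asked | expected (*should*), not observable | uncertain |
| Probably | met | unlikely, as asked | joined by *and*, not observable | not met |
| Potentially | met | grade supposes other factors; here there are none | not asked | poor fit |
| Unlikely | not met: asks for improbable timing | not met: asks for another plausible explanation | not asked | not met |
| Not related | not met | not met: asks for a documented alternative cause | not asked | not met |

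No grade fits cleanly. An investigator who treats dechallenge as not applicable can choose *Definitely* or *Probably*. One who applies the words as written moves to *Potentially*. The same event can then land in different rows of the table.

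**4. Does the upgrade route help?** Section VII.3.3.2 lets an event be raised later from the third grade to one of the top two, but both contain the dechallenge element, so the same obstacle returns.

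**5. What depends on the grade?** Section VII.3.4 has all adverse events up to the end of participation reported to the sponsor whatever their grade, so neither counts nor in-study reporting change. The summary by relationship in VIII.4.3 does depend on it. So does reporting to the sponsor after the end of participation, which VII.3.4 ties to the investigator considering the event related. The plan does not say which grades make up *related*.

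**The case against.** The strongest reply is that the scale does not work alone. The lead-in bases the judgment on timing and clinical judgment and says the device must always be suspected, which pushes grades up. For *Definitely Related* the withdrawal response only *should* be plausible, while the next sentence uses *must*, so a sensible investigator may pass over it when nothing was withdrawn. *Potentially Related* still asserts some evidence of causation, and no rule excludes it from the related events. The analysis is descriptive, and all individual data are listed (VIII.4.1).

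Much of this stands. It rules out three stronger claims that a reader might infer.

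- *That no device-related event can reach the top two grades unless the membrane is removed.* This needs the strictest reading of *Definitely Related*, and the lead-in allows a softer one.
- *That the table is biased downward by construction.* A strict reading leaves a gap between grades, so inconsistent grading is as likely a result as systematic downgrading.
- *That the contribution of the surgery cannot be recorded.* Section VII.3.4 asks each report to include other potential causal factors, and the eCRF is not among the documents. What can be said is that no separate graded relationship to the procedure, and no tabulation by it, is specified.

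The reply does not remove the problem. The lead-in goes on to say that certainty will be graded with the listed categories, and *Probably Related* joins dechallenge to its other conditions with no exception while expressly waiving only rechallenge. Relying on investigators to ignore a written condition is what makes their grades differ.

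**Conclusion.** The point holds in a limited form. The scale requires a dechallenge for *Probably Related* and expects one for *Definitely Related*, and the device cannot routinely supply it. Clear device reactions may therefore be graded too low or inconsistently, which weakens the summary of treatment-emergent events by relationship. Reporting after participation ends is exposed only if a lower grade leads the investigator not to regard the event as related.

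The size cannot be put as a number. The documents give no expected event rate, and the effect depends on how literally investigators read the definitions. The conclusion assumes that the membrane stays in place in most patients with an event, which fits the absence of any planned removal. The primary endpoint, the total event counts, and reporting to the sponsor during the study are not touched. It is worth correcting because the rule as written is unworkable for this device and the correction is cheap.

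**What to change.** In VII.3.3.2, remove the dechallenge condition from *Definitely Related* and *Probably Related*, and the rechallenge clause from *Definitely Related*. Alternatively, keep them but qualify them as applying only where applicable, for example after explantation. *Probably Related* needs no change on rechallenge, since it already waives it.

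Base the two grades on criteria that an implant can meet: timing after placement, location at the implantation site, consistency with the known effects in the instructions for use, and whether another cause is likely.

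In VIII.4.3 and the SAP, state which grades count as device-related in the table of treatment-emergent events.

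Optionally, record and tabulate relationship to the surgical procedure separately from relationship to the membrane. Several expected events in VII.3.3.3, such as post-operative infection and discomfort, could plausibly come from either.

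The cost is protocol and SAP wording and, if the option is taken, one eCRF field per event and one table column. The small downside is that more events may be graded as device-related.
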